having a singleton pregnancy. The midwife will ask the woman if she is willing to participate in the IRIS study and if so, the midwife will ask her to sign the consent form. The form asks the woman's permission for using her personal data for merging data, for collecting detailed information from the woman's and her baby's client records, and for approaching her in the context of future sub-studies. An extra consent form will be added among the subsample of women who will fill in questionnaires. Consent forms will contain name, address, postal code, telephone number, and email and will be kept separate from other data files in a secure place.

Inclusion criteria: receiving

Women who do not have had a dating US will only be included if they have a reliable estimated data of delivery (EDD) based on the first day of their last menstrual period.

The NVOG guideline on US dating of pregnancy will be used for estimation of the EDD.

CONTROL AND INTERVENTION US STRATEGIES

Women in both US strategies will receive routine care as follows:

- Standardised SFH measurement
- Information about life style factors that may influence foetal growth, such as smoking, use of alcohol and drugs, and labour circumstances.
- Advise to report a reduction in fetal movements.
- US examinations on indication

Subsequent protocolised management will be according to the IRIS consensus-based protocol (to be developed in sub-study A).

Intervention US strategy

Additionally, two routine third trimester US examinations will be performed, one between 28 and 30 weeks and one 6 weeks after the first US. By performing two US examinations the growth pattern can be monitored. If a baby does not follow the expected curve, this may indicate a lack of growth even before the abdominal circumference or the estimated fetal weight is low. Subsequent protocolised management will be accomplished according to the IRIS consensus based guidelines.

PRIMARY OUTCOME - SEVERE ADVERSE PERINATAL OUTCOME

The primary clinical outcome is the occurrence of any severe adverse perinatal outcome up to 7 days after birth (yes/no). It concerns a dichotomous composite measure with 'yes' being defined as the presence of one or more of the following:

1. Antepartum, intrapartum or neonatal death occurring from 28 weeks gestation
2. Apgar score below 4 at 5 minutes after birth;
3. Coma, stupor or decreased response to pain;
4. Asphyxia, defined as cord blood arterial base excess of less than minus 12;

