5. Neonatal seizures defined as clonic movements which cannot be stopped by holding the limb, occurring on two or more occasions before 72 hours of age;
6. Assisted ventilation for more than 24 hours via endotracheal tube initiated within 72 hours after birth;
7. Septicaemia, ascertained by a positive blood culture;
8. Meningitis, ascertained by positive cerebrospinal fluid culture;

9. Bronchopulmonary dysplasia (BPD), defined as need for oxygen at a postnatal gestational age from 36 completed weeks as well as an X-ray compatible with BPD;
10. Intraventricular hemorrhage, defined as grade 3 or 4 and diagnosed by cranial US or at autopsy;
11. Cystic periventricular leukomalacia (PVL), diagnosed by cranial US or at autopsy showing periventricular cystic changes in the white matter excluding subependymal and choroid plexus cysts;
12. Necrotizing enterocolitis, defined as either perforation of intestine, pneumatosis intestinalis or air in the portal vein, diagnosed by X-ray, surgery, or at autopsy;

Cord blood arterial base excess was chosen as an indicator of asphyxia because, unlike pH, it is linearly related to the degree of metabolic acidosis which is a better indicator of asphyxia than measures of respiratory acidosis [Ross & Gala, 2002]. There was some discussion in the expert and project group on the use of Apgar scores in the composite outcome. Apgar score in itself is not comparable to the other outcomes, which are more predictive of long term severe adverse outcomes. However, in the Netherlands, a quarter of all women still give birth at home. Suspected SGA is a reason for referral to specialist care and routine US may lead to more SGA babies being born in hospital. Nevertheless, unexpected poor outcomes may occur at home and blood gases immediately after birth will then not be available. In hospital too, cord blood samples may be forgotten or go missing. We have chosen a low cutoff point for Apgar score at five minutes (below 4) in which case most babies will have other adverse outcomes as well. In a recent Dutch RCT on the management of pregnancies complicated by SGA, Apgar scores were also part of the composite outcome [Boers et al., 2010]. Low birth weight is not part of the primary outcome because this is not a measure of morbidity but rather a factor that is associated with morbidity such as respiratory problems. Also, premature labour may sometimes be induced to prevent stillbirth even though prematurity is associated with low birth weight.

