PRIMARY OUTCOME - COSTS

Direct costs will include costs related to pregnancy related healthcare use, such as consultations with the midwife, referrals to specialist care, US scans, laboratory tests; CTG monitoring; hospital admission; interventions during labour; admission to neonatal unit. We will measure absenteeism and presenteeism (indirect costs) by the Productivity Cost Questionnaire (PCQ) [IMTA, Rotterdam]

To value health care utilization, standard costs published in the Dutch costing guidelines will be used [Hakkaart-van Roijen et al., 2011]. Medication use will be valued using prices of the Royal Dutch Society for Pharmacy. The friction cost approach will be used to estimate indirect costs using Dutch age and sex specific lost productivity costs [Koopmanschap & Rutten, 1996; Hakkaart-van Roijen et al., 2011].

SECONDARY OUTCOMES

Composite outcomes

1. Spontaneous vaginal birth without intervention, i.e. a birth without any of the following:
 - induction of labour other than amniotomy
 - vacuum/ forceps
 - caesarean section
 - augmentation of labour
 - pharmacological pain relief: epidural anaesthesia or use of opioids

2. Maternal morbidity, defined as the presence of one or more of the following:

- maternal death within 42 days after giving birth
- hypertension, defined as highest diastolic blood pressure equal or greater than 95
- pre-eclampsia, defined as diastolic blood pressure equal or greater than 90 and proteinuria \geq 300 mg/l
- postpartum haemorrhage $>$ 1000 mL
- third or fourth degree perineal trauma

Singular outcomes

- elements of composite primary outcome
- elements of the two composite secondary outcomes
- neonatal mortality and severe morbidity between 7th and 28th day after birth
- detection of congenital abnormalities
- life threatening congenital conditions born in primary care
- home and hospital birth in primary care
- birth weight: mean; % $<$ P5; % $>$ P95;
- gestational age at birth: mean; % $<$ 37 week
- non-cephalic presentations (when labour started) in primary care
- general quality of life, measured by the EQ-5D-5L [Herdman et al., 2011]
- symptoms of depression, measured by the EPDS [J.L. Cox et al., 1987; Dutch translation: V.J.M. Pop et al., 1992]
- Continuity of health care, measured by the NCQ [A.A. Uijen et al., 2011]
- Satisfaction with health care, measured by the PCQ [S.E.M. Truijens et al., 2014]

OTHER OUTCOMES

Descriptive variables and predictors of outcome

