Firstly, we will conduct a pregnancy related cost-effectiveness analysis from a health care provider perspective. The time horizon of this analysis is from 26 weeks of gestation until one week after the date of birth. In this analysis, pregnancy related data of all 15,000 women will be included, using the PRN data. Detailed cost data collected by the research midwives on the 600 random and 400 selected women will be used to estimate the pregnancy related direct costs for the whole group of 15,000 women by using Bayesian techniques in combination with Monte Carlo simulation. These costs will be related to a composite of severe adverse perinatal outcome to estimate the Incremental Cost-Effectiveness Ratios (ICER).

Secondly, we will conduct a cost-effectiveness analysis from a societal perspective. The time horizon of this analysis is from 22 weeks gestation until 6 months after the EDD. In this analysis, pregnancy related data of all 15,000 women will be included, using the PRN data. Detailed cost data collected on the 600 random and 400 selected women will be used to estimate the pregnancy related direct costs for the whole group of 15,000 women by using Bayesian techniques in combination with Monte Carlo simulation. Furthermore, the combination of direct and indirect costs will be related to a composite of severe adverse perinatal outcome to estimate the Incremental Cost- Effectiveness Ratios (ICER).

Finally, we will conduct a cost-utility analysis from a societal perspective. The time horizon of this analysis is from 22 weeks gestation until 6 months after the expected date of birth. In this analysis, solely data of the 600 randomly selected women participating in the survey study will be included. To estimate outcomes more precisely for women in the random sample with suspected IUGR, we will additionally use the data of the 400 women in the selective sample. Costs will be related to Quality-Adjusted Life-Years based on the EQ-5D-5L using the Dutch tariff to estimate the Incremental Cost-Utility Ratio (ICUR).[Lamers et al., 2005] In this analysis, missing cost and effect data will be imputed using multiple imputation according to the MICE algorithm developed by Van Buuren and colleagues (1999).

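### The provider-perspective cost-effectiveness analysis stops costs one week after birth and so omits an unquantified part of the neonatal cost of the outcomes it counts

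*Protocol*

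**What the plan says.** All references are to the Protocol.

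- **Horizon.** Under Cost-effectiveness and cost-utility analyses, the first (provider) analysis has this limit: "The time horizon of this analysis is from 26 weeks of gestation until one week after the date of birth". No reason for the end point is given.
- **Ratio.** The same paragraph continues: "These costs will be related to a composite of severe adverse perinatal outcome to estimate the Incremental Cost-Effectiveness Ratios (ICER".
- **Effect.** The section PRIMARY OUTCOME - SEVERE ADVERSE PERINATAL OUTCOME defines the event as follows: "The primary clinical outcome is the occurrence of any severe adverse perinatal outcome up to 7 days after birth (yes/no". Its components include "Assisted ventilation for more than 24 hours via endotracheal tube initiated within 72 hours after birth", septicaemia, meningitis, severe intraventricular haemorrhage and necrotizing enterocolitis. They also include death before, during or after birth.
- **Costs.** The direct costs listed under PRIMARY OUTCOME - COSTS include scans, referrals and "hospital admission; interventions during labour; admission to neonatal unit".
- **Later morbidity.** SECONDARY OUTCOMES lists "neonatal mortality and severe morbidity between 7th and 28th day after birth".
- **Second analysis.** The societal cost-effectiveness analysis uses the same composite and all 15,000 women. It runs from 22 weeks to 6 months after the expected date of delivery, and relates direct and indirect costs together to the composite.
- **Sensitivity analyses.** Two are planned: a per-protocol analysis, and a repeat in the 600 randomly sampled women only.

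**The concern.** An event within the first week counts in full in the denominator of the provider ICER, but its hospital care counts in the numerator only to day 7. What routine scanning adds before birth (the scans, extra monitoring, referrals) lies wholly inside the horizon, since the first routine scan is at 28 to 30 weeks and costs start at 26 weeks. What it may save or add in neonatal care lies only partly inside.

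The cut works in both directions. If severe outcomes are averted, part of the saving is lost. If suspected growth restriction leads to more elective delivery, a harm the protocol raises under ADVERSE EFFECTS OF US SCREENING, part of the cost of any resulting neonatal admission is lost.

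Costs are a primary outcome and cost-effectiveness is the second objective. The provider result is one of the two cost-effectiveness results the protocol promises for the full 15,000 women.

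**Working it through.** **Figures available.** The protocol states no length of stay, daily cost or ICER, so there is no cost figure to reproduce. The one checkable figure nearby is the sample size behind the target effect. For 1.54% versus 1.0%, 80% power and a two-sided 0.05 level, the usual two-proportion formula without continuity correction gives 6,749 per group, or 13,498 in total, against the stated 13,536. That agrees closely enough to take the target risk difference as E = 0.0154 − 0.0100 = 0.0054. With 7,500 women per strategy this is 115.5 versus 75.0 expected cases, a difference of 40.5.

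**Time left for costs after a qualifying event.**
- Ventilation may start as late as 72 hours and must exceed 24 hours. A late starter qualifies after 72 + 24 = 96 hours, at the end of day 4, which leaves 7 − 4 = 3 days of counted cost.
- An infection or necrotizing enterocolitis arising on day 6 leaves 7 − 6 = 1 day.

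So events that fall inside the effect window can have most of their care still ahead of them when costing stops. How often this happens is not stated.

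**Share of one stay left out.** For a stay of L days from birth at constant daily cost, the share is max(0, L − 7)/L. The values of L are assumptions.

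| Stay L (days) | Days left out | Share left out |
|---|---|---|
| 7 or less | 0 | 0% |
| 10 | 3 | 30% |
| 14 | 7 | 50% |
| 21 | 14 | 67% |
| 28 | 21 | 75% |

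If the first days cost more per day than later ones, the shares are smaller. Across babies, the share is the sum of days after day 7 over the sum of all days, so it depends on the spread of stays and not only on their mean.

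**Effect on the ICER.** Let K be the cost difference per woman up to day 7 (intervention minus control), D the difference in neonatal days after day 7 per woman, and c the daily cost.
- Planned: K/E.
- With later neonatal days included: (K + cD)/E.
- Planned minus complete: −cD/E.

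If D is negative (days saved), the planned ICER is too high; if D is positive, it is too low. Where each averted case saves on average m days after day 7, D = −mE, and the planned ICER is too high by m × c per case averted: 3c for m = 3, 7c for m = 7, 14c for m = 14. Here m is a net average over all averted cases. An averted antepartum death saves no neonatal days and may add some, so even the sign of m is not given by the documents.

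**The case against.** The strongest reply is that the evaluation as a whole is not truncated. The societal analysis uses the same composite and the same 15,000 women, and runs to 6 months after the expected date of delivery, long enough to take in neonatal care to discharge for almost any baby. The cost-effectiveness objective is not confined to the provider perspective. A short, pregnancy-related provider analysis beside a longer societal one is a recognisable plan, and in the short one costs and effects end on the same day.

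Much of this stands, and it limits the point to the provider result. It does not remove it. The societal ICER combines direct with indirect costs, so it cannot be read as what a provider or insurer would pay. Matching end dates also do not settle the matter: the effect window limits when an event may occur, not how long its care lasts.

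Two stronger readings are tempting. A reader might infer that most of the neonatal cost is lost, or might multiply the 40.5 cases by an assumed stay to get a total of missed hospital days. Neither is supported. No stay is given, and the composite is not broken down by component. It includes deaths before or during birth with no neonatal stay, and cases of low Apgar score or abnormal base excess whose stay is unknown.

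A reader might also point to bronchopulmonary dysplasia, "defined as need for oxygen at a postnatal gestational age from 36 completed weeks". A baby born at 30 weeks reaches that age on day 42, outside the 7-day effect window. On the stated window such a baby counts only through another component, so this is not a fair example of a counted outcome with truncated cost.

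**Conclusion.** The point holds in limited form. Following the plan gives a provider ICER that omits neonatal hospital cost after day 7 for outcomes it counts in full, and for admissions that follow earlier delivery, while antenatal costs from 26 weeks are complete. The omitted part may be large, but its size is unknown: the 0% to 75% range above rests on assumed stays of 7 days or less up to 28 days and a constant daily cost. The direction of the net bias is also unknown, because averted morbidity, averted stillbirth and added early deliveries pull different ways. It would therefore go too far to say that the provider result is biased against scanning, or that the economic evaluation as a whole fails. The clinical primary analysis is unaffected. What is missing from the protocol is any provider-only result over a period long enough to show whether the cut-off matters.

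**What to change.** In Cost-effectiveness and cost-utility analyses, add a provider-perspective ICER with direct costs only, over the horizon already set for the societal analysis, and report it beside the one-week result. Direct costs for all 15,000 women are already estimated for that analysis, so the extra result is mainly a reporting step. An alternative is to extend the provider horizon to a fixed point such as day 28, which matches the existing secondary outcome on later morbidity.

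The data are largely planned. Existing databases are to supply days in hospital for all women, and hospital records are to be reviewed for the care of babies referred for neonatal admission and babies with a severe outcome (DATA COLLECTION). The protocol should add that this review records length and level of neonatal stay up to the chosen end point.

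The cost is a little more analysis and abstraction work, and a more variable cost estimate, because a few long stays will carry weight.

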Thirdly, a random sample of 450 women receiving the intervention US strategy and 450 women receiving the control US strategy will be asked to complete questionnaires at 22 and 32 weeks gestation during pregnancy, and at 6 weeks and 6 months after EDD (n= 15 per midwifery practice). Additionally, a non-random sample consisting of 600 women in whom IUGR is suspected by ultrasonography (300 intervention and 300 control women) will be asked to complete questionnaires (n= 10 per midwifery practice). Assuming a non-response and drop-out rate of 33% we aim to collect follow-up data on 1000 women. Questionnaires will collect detailed information on healthcare utilization related to the pregnancy, type of work, absenteeism and presenteeism (PCQ), quality of life (EQ-5D-5L), satisfaction with health care (PCQ), continuity of health care (NCQ) and depression (EPDS). To minimise non-response the baseline questionnaire will be handed to the women by their midwife. Women will receive an email with a link to online follow-up questionnaires. Non-responders will be contacted by telephone and/or receive a postal follow-up questionnaire. To enhance participation from women from various ethnic backgrounds and socio-economic positions interviewers who speak Dutch, English, Turkish and/or Moroccan will be available to fill in the questionnaire by telephone if women need assistance.

Lastly, research midwives/nurses will collect detailed information from hospital medical records on 1) clinical outcomes and care process of babies who are referred to a pediatrician for neonatal admission; 2) clinical outcomes and care process of babies with severe adverse perinatal outcome according to data of existing databases and 3) pregnancy related health care utilization of women participating in the questionnaire study (n=1000).

DATA MONITORING AND EVALUATION

Data will be checked for missing values and irregularities. US management of midwifery practices will be checked at least two times during the recruitment period.

STATISTICAL ANALYSES

Sample size of full trial

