Both cost-effectiveness and cost-utility analyses will be done according to the intention-to-treat principle. ICERs and the ICUR will be calculated by dividing the difference in mean costs between the two groups by the difference between the two groups in effects and in QALYs, respectively. Bias-corrected and accelerated bootstrapping with 5000 replications will be used to estimate 95% confidence intervals around cost differences and the uncertainty surrounding the ICERs and ICUR. Uncertainty surrounding the ICERs and ICUR will be graphically presented on cost-effectiveness planes. Cost-effectiveness acceptability curves will also be estimated using the net benefit framework.[Stinnett & Mullahy, 1998] Cost-effectiveness acceptability curves show the probability that routine third trimester ultrasound screening to detect IUGR is cost-effective in comparison with usual care for a range of different ceiling ratios thereby showing decision uncertainty.

We will perform a subgroup analysis for women without US indication and for nulliparous women.

We will explore the robustness of the results of our intention to treat analysis by a per-protocol sensitivity analysis. Furthermore, we will repeat the pregnancy related cost-effectiveness analysis from a health care provider perspective and the cost-effectiveness analysis from a societal perspective using solely the data of the 600 randomly selected women participating in the survey study.

REFERENCES

Alfirevic Z, Stampalija T, Gyte GM. Fetal and umbilical Doppler ultrasound in high-risk pregnancies. *Cochrane Database Syst Rev* 2010a;(1):CD007529.

Alfirevic Z, Stampalija T, Gyte GM. Fetal and umbilical Doppler ultrasound in normal pregnancy. *Cochrane Database Syst Rev* 2010b;(8):CD001450.

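### The cost-utility analysis names no adjustment of the QALY difference for the 22-week EQ-5D-5L, a value recorded before the first routine scan that is also the first point of the QALY

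*Protocol*

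**What the plan says.** All references are to the protocol.

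- **Estimator** (Cost-effectiveness and cost-utility analyses): "ICERs and the ICUR will be calculated by dividing the difference in mean costs between the two groups by the difference between the two groups", for effects in the ICERs and for QALYs in the ICUR. Uncertainty comes from a bias-corrected and accelerated bootstrap with 5000 replications. The section names no regression model or covariate for the QALY difference.
- **Horizon** (same section): "The time horizon of this analysis is from 22 weeks gestation until 6 months after the expected date of birth". QALYs come from the EQ-5D-5L with the Dutch tariff, and missing costs and effects are imputed with MICE.
- **Sample** (same section): "In this analysis, solely data of the 600 randomly selected women participating in the survey study will be included". Data from 400 selectively sampled women are used in addition, to sharpen the estimates for women with suspected IUGR.
- **Measurement times** (Data collection, Forms and surveys): the random sample "will be asked to complete questionnaires at 22 and 32 weeks gestation during pregnancy, and at 6 weeks and 6 months after EDD". The first form is treated as a baseline: "To minimise non-response the baseline questionnaire will be handed to the women by their midwife".
- **Start of the contrast** (Intervention US strategy): "two routine third trimester US examinations will be performed, one between 28 and 30 weeks and one 6 weeks after the first US". The 22-week form therefore comes before any routine third-trimester scan.
- **Adjustment elsewhere** (Effectiveness analyses): a multilevel logistic model with example confounders is planned for perinatal outcome. Utility is not among the examples, and the paragraph does not extend to QALYs.

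**The concern.** The 22-week utility enters the QALY in two ways. It is the first point of the area under the curve, and it can be expected to correlate with each later utility. If the QALY difference is taken without regard to it, a difference in utility that was present before the first routine scan is counted as part of the result for routine ultrasound. The variation that the baseline value could explain stays in the standard error.

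Imbalance at 22 weeks is credible in this design:

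- Women are not individually randomised. They are invited after the order in which practices cross over has been drawn.
- Practices move in one direction at 3-month intervals, so control and intervention women differ in calendar time.
- The survey assumes 33% non-response and drop-out.

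Cost-effectiveness is one of the two main trial objectives. The QALY difference is the denominator of the ICUR and feeds its acceptability curve. It rests on about 600 of 15,000 women, so precision is scarce. Leaving the choice open also allows an adjusted or an unadjusted ICUR to be chosen after the results are known.

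**Working it through.** **1. The plan's own figures.** No power, SD or correlation is stated for QALYs, so there is no QALY figure to reproduce. The survey numbers do reproduce: 450 + 450 = 900 women, and 900 × 0.67 = 603, against the stated 600. For the selective sample, 600 × 0.67 = 402, against the stated 400. The check below uses 300 women per strategy.

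**2. Weight of each questionnaire.** Taking the EDD as 40 weeks, the four forms fall at weeks 22, 32, 46 and 66. The intervals are 10, 14 and 20 weeks. The trapezoid rule gives weights of 5, 12, 17 and 10 weeks, total 44. The 22-week value carries 5/44 = 11.4% of the QALY directly.

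**3. Assumptions.** Equal utility SD at all four times, a common between-visit correlation r of 0.3, 0.5 or 0.7, and no clustering. None of these comes from the protocol.

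**4. Formulas,** in weeks and per unit of utility variance:

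- Covariance of baseline with QALY: c = 5 + r(12 + 17 + 10) = 5 + 39r
- Variance of QALY: the squared weights sum to 25 + 144 + 289 + 100 = 558, and 44² = 1936, so v = 558 + r(1936 − 558) = 558 + 1378r
- QALY shift per unit of baseline difference: c/52
- Baseline–QALY correlation: ρ = c/√v
- Variance removed by adjustment: ρ²; SE ratio, adjusted to unadjusted: √(1 − ρ²)

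| r | c | v | Shift per unit d | ρ | Variance cut | SE ratio |
|---|---|---|---|---|---|---|
| 0.3 | 16.7 | 971.4 | 0.32 | 0.54 | 29% | 0.84 |
| 0.5 | 24.5 | 1247.0 | 0.47 | 0.69 | 48% | 0.72 |
| 0.7 | 32.3 | 1522.6 | 0.62 | 0.83 | 69% | 0.56 |

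**5. On the QALY scale.** A 22-week difference of 0.02 moves the unadjusted QALY difference by 0.0064, 0.0094 or 0.0124 for r = 0.3, 0.5 or 0.7.

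The unadjusted SE is SD × (√v/52) × √(2/300). Unadjusted → adjusted SE:

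| Utility SD | r = 0.3 | r = 0.5 | r = 0.7 |
|---|---|---|---|
| 0.10 | 0.0049 → 0.0041 | 0.0055 → 0.0040 | 0.0061 → 0.0034 |
| 0.15 | 0.0073 → 0.0062 | 0.0083 → 0.0060 | 0.0092 → 0.0052 |
| 0.20 | 0.0098 → 0.0083 | 0.0111 → 0.0080 | 0.0123 → 0.0069 |

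Example with SD 0.20 and r = 0.5: the SE of the baseline difference is 0.20 × √(2/300) = 0.0163. An imbalance of one such SE moves the QALY difference by 0.0163 × 0.471 = 0.0077, against an unadjusted SE of 0.0111.

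**The case against.** **The sentence is only a definition.** It is the usual definition of an ICER or ICUR. It says which quantities are divided, not how each difference is estimated. In it, the word mean qualifies costs only, and nothing calls the QALY difference crude or unadjusted. A regression-adjusted difference would fit it. This stands: a reader might infer that the protocol prescribes a raw difference in means, and the text does not go that far.

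**Such detail is commonly left to a statistical or health-economic analysis plan,** and none is shown. This stands in part, since silence alone would be no error. But the protocol already fixes the tariff, horizon, sample, imputation method, and bootstrap type and number, and for perinatal outcome it writes the adjustment into the text. Someone following the economic section as it stands would compute an unadjusted difference. The point is an improvement at almost no cost, not a contradiction.

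**Chance imbalance is not bias.** This stands. A reader might infer that any 22-week difference biases the ICUR. Chance imbalance adds variance, which the bootstrap interval already reflects, and adjustment then gains precision. Only a systematic difference, through calendar time or non-response, would bias the result, and the documents give no evidence of its size. Nor is strategy simply confounded with practice: every practice starts in control and later crosses over.

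**Gains in power, or a comparison with a plausible effect, cannot be claimed.** This stands. The protocol states no power and no expected effect for QALYs, and it presents uncertainty through planes and acceptability curves.

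**The selectively sampled women complicate the fix.** This stands. The stated questionnaire times are attached to the random sample. Women selected because IUGR is suspected may have no 22-week value recorded before that suspicion. The fix needs a rule for them.

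**Conclusion.** The point holds as a recommended change to the analysis. The protocol collects a utility before the first routine scan, makes it part of the QALY, and provides no adjustment of the QALY difference for it. Under an assumed between-visit correlation of 0.3 to 0.7, between about a third and three fifths of a 22-week difference in utility, in QALYs per unit of utility, would pass into the denominator of the ICUR. The unadjusted SE would be about 1.2 to 1.8 times the adjusted one (1/0.844 to 1/0.561).

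These figures rest on the trapezoid rule, equal SDs, a common correlation, 300 women per strategy and no clustering. They also leave out the 400 selectively sampled women. The proportional results do not depend on the SD; the absolute SEs do. The documents do not support saying that the protocol rules out adjustment, or that a systematic imbalance exists.

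**What to change.** In the section on cost-effectiveness and cost-utility analyses, add the following:

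- Estimate the QALY difference in the ICUR as the strategy coefficient from a regression of QALYs on strategy and 22-week EQ-5D-5L utility in the random sample.
- Refit this model in each bootstrap sample, and keep the 22-week value in the MICE model.
- Use the adjusted difference in the ICUR, its cost-effectiveness plane and its acceptability curve. Report the unadjusted difference as a sensitivity analysis.
- For the selectively sampled women with suspected IUGR, use a 22-week value only if it was recorded before suspicion arose; otherwise treat it as missing.

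**Cost.** Wording and a modest amount of programming, with no new data collection. Women without a usable 22-week form depend on the multiple imputation already planned. For the selective sample that dependence could be considerable, and the date on which suspicion arose must be available to apply the rule.
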